#### **Outcome**

Each AE will be characterized according to the outcomes described in the following table:

| Outcome                          | Description   |
|----------------------------------|---|
| Recovered/Resolved               | The subject has fully recovered from the event with no observable residual effects.   |
| Recovering/Resolving             | The effects of the event are improving, or events have stabilized (are constant and not expected to improve or worsen) but have not returned to baseline. |
| Not recovered/Not Resolved       | The effects of the event are still present and changing. The event is not considered stabilized or resolved.  |
| Recovered/Resolved with Sequelae | The subject has fully recovered from the event with some observable residual effects.   |
| Fatal                            | The event was the primary cause of death (may or may not be the immediate cause of death).  |
| Unknown                          | The event outcome is unknown.   |

Death is an outcome of an event and not an event *per se*. Sudden death or death due to unexplainable cause(s) is to be reported, but follow-up will be pursued until cause of death is determined.

## **Action Taken with Study Drug**

Action taken with study drug in relation to each adverse event will be characterized as follows:

- None
- Drug withdrawn
- Drug interrupted
- Dose reduction
- Unknown
- Not applicable
- Other (specify on eCRF)

#### 9.3 Serious Adverse Events

Any AE that is serious (see definition below) and occurs after administration of study drug must be reported to the CRO Medical Monitor within 24 hours of discovery of the event. An event occurring after informed consent but before administration of study drug that is considered serious and possibly related to a protocol procedure must also be reported to the CRO within 24 hours of discovery of the event.

## 9.3.1 Definition and Reporting Procedures

An AE should be classified as an SAE if it meets one of the following criteria:

| Fatal:            | The adverse event resulted in death.  |
|-------------------|---|
| Life Threatening: | The adverse event placed the subject at immediate risk of death. This classification does not apply to an adverse event that hypothetically might cause death if it were more severe. |

| Fatal:                              | The adverse event resulted in death.  |
|-------------------------------------|---|
| Hospitalization:                    | The adverse event required or prolonged an existing inpatient hospitalization. Hospitalizations for elective medical or surgical procedures or treatments planned before the signing of informed consent in the study or routine check-ups are not serious adverse events by this criterion. Hospitalizations or prolonged hospitalizations for scheduled therapy need not be captured as SAEs. |
| Disabling/Incapacitating:           | Resulted in a substantial and permanent disruption of the subject's ability to carry out activities of daily living.  |
| Congenital Anomaly or Birth Defect: | An adverse outcome in a child or fetus of a subject exposed to the study drug or study treatment regimen before conception or during pregnancy.   |
| Medically Significant:              | The adverse event did not meet any of the above criteria, but could have jeopardized the subject and might have required medical or surgical intervention to prevent one of the outcomes listed above.  |

Every SAE (regardless of suspected causality) should be reported to the CRO Medical Monitor within 24 hours of discovery of the event. The processes for reporting and documenting SAEs are provided in the study manual. Investigators are responsible for reporting these events to their Institutional Review Board/Institutional Ethics Committee (IRB/IEC) in accordance with federal and institutional laws and regulations.

Additional updates from the Investigator may be necessary as more information becomes available on the SAE, and all treatment-related SAEs will be followed until the acute event has resolved or stabilized, even if the subject discontinues study participation prior to the SAE resolution. Any new information or follow-up information pertaining to previously reported SAEs will be reported to the CRO Medical Monitor within 24 hours of becoming aware of the new or follow-up information. The new or follow-up information should be faxed to [contact] (US toll-free: [name]) or e-mailed to [contact].

Any SAE that occurs after study completion, and is considered by the Investigator to be related to sofpironium bromide, should be reported to the Sponsor.

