#### **Intensity**

The following definitions should be used to assess and grade AE intensity, including laboratory abnormalities judged to be clinically significant.

| Severity | Grade | Description   |  |  |
|----------|-------|---|--|--|
| Mild     | 1     | Awareness of sign or symptom, but easily tolerated          |  |  |
| Moderate | 2     | Discomfort enough to cause interference with usual activity |  |  |

| Severity | Grade | Description  |
|----------|-------|--|
| Severe   | 3     | Incapacitating with inability to work or do usual activity |

Note: a severe adverse event is not necessarily serious.

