## 9.4 Follow-up of Adverse Events and Laboratory Test Abnormalities

AE information will be collected during the clinical trial from the time the subject signs informed consent through the final study visit. SAEs that are considered related to study drug by the Investigator or Sponsor should be followed until the events resolve or stabilize.

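### The disability criterion for a serious adverse event requires permanence, so an incapacitating reaction that resolves is not serious under that criterion

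*Protocol*

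**What the plan says.** Protocol Section 9.3.1 sets out six rows and makes any one of them sufficient: "An AE should be classified as an SAE if it meets one of the following criteria". The rows are Fatal, Life Threatening, Hospitalization, Disabling/Incapacitating, Congenital Anomaly or Birth Defect, and Medically Significant. The fourth reads "Resulted in a substantial and permanent disruption of the" subject's capacity for daily living. The sixth takes in events that met none of the others but could have put the subject in jeopardy and might have called for intervention to avert an outcome in the rows above it.

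On timing, Section 9.3.1 states: "Every SAE (regardless of suspected causality) should be reported to the CRO Medical Monitor within 24 hours of discovery of the event". Section 9.3 says of serious events after dosing that they "must be reported to the CRO Medical Monitor within 24 hours of discovery of the event". The sponsor then decides which SAEs go to regulators on an expedited basis (Section 9.3.1, under the heading on reporting to regulatory agencies).

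Severity is graded separately. In Section 9.2.1.2, under Intensity, Grade 3 is "Incapacitating with inability to work or do usual activity". No duration is attached, and a note says that a severe event need not be serious. On follow-up, Section 9.4 states: "SAEs that are considered related to study drug by the Investigator or Sponsor should be followed until the events resolve or stabilize". The SAP contains no SAE definition of its own.

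**The concern.** The disability row is the only one that classes an event as serious directly because of what it does to the subject's functioning. Tying it to permanence means that a reaction which stops a subject working or carrying out usual activity, and then clears, does not qualify under it. The protocol uses incapacitating for both states without saying how the two thresholds relate, so an investigator with a Grade 3 event has no guidance on whether the disability row applies.

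The classification has consequences. It decides whether the event is reported within 24 hours, whether it reaches the sponsor's expedited-reporting review, and whether it appears in the SAE tables and listing. The question is relevant to this drug because the protocol's Risk to Subjects section describes the expected anticholinergic effects as transient. Should one of them be incapacitating, a permanence test would not be met.

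**Working it through.** No arithmetic applies. The check is a reading of the definitions side by side, followed by one hypothetical case taken through every row.

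**Step 1: the two uses of incapacitating.**

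| Place | Condition on function | Condition on duration |
|---|---|---|
| Section 9.2.1.2, Grade 3 | Unable to work or do usual activity | None |
| Section 9.3.1, Disabling/Incapacitating | Substantial disruption of daily living | Permanent |

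The second row joins its conditions with *and*. I found nothing in the protocol or SAP that relaxes permanent to persistent, prolonged or temporary. A temporary event therefore fails this row whatever its intensity. That follows from the one word and does not depend on the reporting deadline.

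**Step 2: the deadline.** In both Section 9.3 and Section 9.3.1 the 24 hours run from discovery of the event. No text says how permanence is to be judged in that time. For most drug reactions it cannot be. This is a second difficulty, affecting also those events that later prove lasting.

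**Step 3: a test case against all six rows.** Take a Grade 3 reaction that prevents usual activity for a period and then resolves, with no hospital admission and no danger to life.

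- Fatal: not met.
- Life Threatening: not met.
- Hospitalization: not met.
- Disabling/Incapacitating: substantial, but not permanent, so not met.
- Congenital Anomaly or Birth Defect: not applicable.
- Medically Significant: depends on the event. The row refers to any of the five outcomes above it, so an event that might have needed intervention to prevent hospitalization is serious with no question of permanence. It is worded conditionally, so no intervention need actually have been given. If there was no jeopardy and no listed outcome to prevent, the row is not met.

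The residual gap is therefore the self-limiting incapacitating event without jeopardy and without a preventable listed outcome.

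**Step 4: where such an event still appears.** It is recorded as an adverse event. If treatment-emergent, it is tabulated under all TEAEs and severe TEAEs (Protocol Section 10.4, SAP Section 9.2). If it is one of the events of special interest or an anticholinergic event, it also has its own table and listing. It would be absent from the SAE tables and listing, the 24-hour report and the expedited-reporting review.

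**The case against.** The strongest reply is that the practical gap is narrow and the safety signal is kept. Four parts of it stand.

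- **Medically Significant is a real backstop.** A reader might infer that it fails because the disability outcome it refers to is again the permanent one. The text does not support that: hospitalization is also among the listed outcomes and carries no permanence condition. It would be wrong to say that reversible incapacitating events are never serious.
- **Some harms are plainly permanent at once.** A reader might infer that the row can be applied to no event within 24 hours. That is too absolute; the difficulty holds for most drug reactions, not all.
- **The obvious examples are closely tracked.** Blurred vision, mydriasis and urinary hesitation are events of special interest in SAP Section 9.2, with tables at successive visits, a line in the overall summary and a separate listing. They would not disappear from the report.
- **Late awareness is not shown.** Adverse events are reviewed at every visit from Visit 2, and Protocol Section 7.4 has the sponsor told of early discontinuation as soon as possible. These are not 24-hour routes, but they rule out an unqualified claim that the sponsor would learn late.

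The documents also suggest few candidates. Section 1 reports over 1300 subject exposures, six serious events all judged unrelated, and anticholinergic events that were mostly mild or moderate and transient. That limits the likely number. It does not remove the mismatch, and those past serious-event figures do not show which seriousness definition was used to collect them.

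**Conclusion.** The point holds, limited to this criterion. As written, a reversible incapacitating reaction is not serious under Disabling/Incapacitating, and if no other row applies it can miss the serious classification, the 24-hour report and the expedited-reporting review. This rests on reading permanent in its ordinary sense and on the absence of any text that qualifies it.

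The number of events affected cannot be derived and may be small. A reader might go on to infer that serious-event counts in this trial are understated; no document shows that any event has been missed. Nor can it be said that the row departs from the regulatory and ICH sources cited in Section 9.2.1, since their text is not reproduced. No efficacy endpoint, sample size or efficacy analysis is touched. The change is worth making because it is cheap and concerns the channel through which serious harms reach the sponsor.

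**What to change.** In the Section 9.3.1 table, remove the permanence condition from the Disabling/Incapacitating row, so that a substantial disruption of the subject's ability to manage daily living qualifies whether or not it is permanent. Reconcile that row with the Grade 3 wording in Section 9.2.1.2, so that investigators can see how an incapacitating event is to be judged for severity and for seriousness. Use the same wording in the SAE form instructions.

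The cost is one table cell and matching form text, with a few more events classed and reported as serious. If events have already been recorded under the present wording, a blinded review of Grade 3 events against the revised row before database lock would correct their classification, though it could not restore a 24-hour report.

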#### **Reporting Serious Adverse Events to Regulatory Agencies**

The Sponsor will determine which SAEs qualify for expedited reporting to regulatory agencies. SAEs that qualify for expedited reporting will be submitted to regulatory agencies in accordance with federal regulation (21 CFR 312.32).

## 9.4 Follow-up of Adverse Events and Laboratory Test Abnormalities

AE information will be collected during the clinical trial from the time the subject signs informed consent through the final study visit. SAEs that are considered related to study drug by the Investigator or Sponsor should be followed until the events resolve or stabilize.

## 9.5 **Pregnancy Reporting**

Sexually active females of childbearing potential (FOCBP)\* must have a negative pregnancy test prior to study enrollment and must use an acceptable method of contraception during the course of the study, in a manner such that risk of failure is minimized. Prior to study enrollment, FOCBP must be advised of the importance of avoiding pregnancy during trial participation and the potential risk factors for an unintentional pregnancy. The subject must sign an informed consent form documenting this discussion.

FOCBP must agree to periodic pregnancy testing and use a medically acceptable method of contraception for the duration of the study. This includes perimenopausal women who are <12 months from their last menses. Acceptable contraceptive methods include the following:

- Abstinence for the duration of the study or where partner is sterile (e.g., vasectomy); OR
- Hormonal contraception, including oral, injectable, or implantable methods started ≥2 months prior to screening; OR
- Non-hormonal contraception, including IUD (≥1-week status post placement) or properly used barrier methods (e.g., male or female condoms with or without spermicide, cervical cap/diaphragm with spermicide).
- \* FOCBP for this study includes any premenopausal female capable of becoming pregnant who has not undergone successful surgical sterilization (hysterectomy, bilateral tubal ligation [≥6 months prior to baseline] or bilateral oophorectomy) or is not postmenopausal (defined as amenorrhea ≥12 consecutive months).

Subjects who become sexually active or begin to have relations with a partner who is not sterile during the trial must agree to use an acceptable form of birth control for the duration of the study.

## 9.5.1 Time Period for Collecting Pregnancy Information

FOCBP should be instructed to contact the Investigator immediately if they suspect they might be pregnant (e.g., missed or late menstrual period). If a subject or Investigator suspects that a subject may be pregnant at any time during the study, the investigational product must be withheld until the results of laboratory pregnancy testing are available. If pregnancy is confirmed, the subject must not receive or apply further investigational product and must be discontinued from the study.

## 9.5.2 Action to Be Taken If Pregnancy Occurs

If following initiation of investigational product, it is subsequently discovered that a trial subject was pregnant or may have been pregnant at the time of investigational product exposure, the Investigator must immediately notify the CRO Medical Monitor of this event, and record the pregnancy on the appropriate pregnancy surveillance form. The form will be sent to the CRO Medical Monitor by fax to [contact] (US toll-free: [name]) or e-mailed to [contact]. The Investigator must notify the IRB of any pregnancy associated with the study therapy and keep careful source documentation of the event.

Protocol-required procedures for those subjects that are discontinued from the study must be performed on the subject unless contraindicated by pregnancy (e.g., x-ray studies). Other appropriate pregnancy follow-up procedures should be considered if indicated, including counseling of the subject by the Investigator and her managing physician or health care provider (e.g., obstetrician). In addition, the Investigator must report to the CRO Medical Monitor, on the appropriate pregnancy surveillance form(s), any follow-up information regarding the course of the pregnancy, including perinatal (period immediately before and after birth) and neonatal (infants up to 28 days after birth) outcome.

Although pregnancy itself is not an AE, any complications during pregnancy should be recorded as AEs (or SAEs, if they fulfill the SAE criteria). **Offspring will be followed for a minimum of eight weeks.** Any congenital anomaly/birth defect in a child born to a subject exposed to the test article(s) will be recorded as a SAE and details documented in the pregnancy surveillance form. An abortion, whether accidental, therapeutic, elective or spontaneous, will be reported as a SAE.

## 9.6 Other Safety Measures

Safety will also be assessed by physical examinations, laboratory tests, and measurement of vital signs assessed as indicated throughout the study schedule. Clinically significant changes in these parameters may be captured as adverse events.

#### 10 STATISTICAL PROCEDURES

A detailed statistical analysis plan (SAP) will be generated prior to the final database lock. Database lock will follow completion of data entry, verification and validation, database audit, and data clarification resolution.

## 10.1 Analysis Populations

The three analysis populations for this study are defined below. Identification of the subjects to be included in each analysis population will be determined and finalized prior to database unmasking.

## **10.1.1 Intent-to-Treat Population**

The Intent-to-Treat (ITT) Population will include all subjects who were randomized. Subjects will be analyzed according to the treatment group to which they were randomized, regardless of post-randomization protocol deviations, including no treatment or wrong treatment received.

## 10.1.2 Per-Protocol Population

The PP Population will be a subset of the ITT Population and will include subjects who meet the following criteria:

- Meets all inclusion/exclusion criteria
- Has not taken or applied any interfering concomitant medications
- Completed the following visits:
  - Visit 2 GSP 1, and the required GSP data collection
  - o Visit 3 GSP 2, and the required GSP data collection
  - Visit 4 (Day 1) Re-screening/Baseline GSP 3 and HDSM-Ax, and the required GSP and HDSM-Ax data collection
  - $\circ$  Visit 10 (GSP 4) Day 41 ( $\pm$  2 days), and the required GSP data collection
  - $\circ$  Visit 11 (GSP 5) Day 42 ( $\pm$  2 days), and the required GSP data collection
  - Visit 12 (GSP 6) Day 43 (± 2 days) and HDSM-Ax, and the required GSP and HDSM-Ax data collection

#### 10.1.3 Safety Population

The Safety Population will include all subjects randomized in the study who received study drug, either vehicle or sofpironium bromide gel, 15%, at least once. If a subject received any sofpironium bromide gel, 15%, the subject will be analyzed in the sofpironium bromide gel, 15%, treatment group. Otherwise the subject will be included in the vehicle group.

## 10.2 Efficacy Endpoints

#### 10.2.1 Definitions

For the purposes of analysis, Baseline and End of Treatment (EOT) definitions for the two primary efficacy assessment measures, HDSM-Ax-7 and Gravimetric Sweat Production (GSP), are defined below.

#### **HDSM-Ax**

- Baseline = Visit 4 (Day 1) assessment
- EOT = Visit 12 (Day 43) assessment

#### **GSP**

- Baseline = the median of GSP1, GSP2, and GSP3 measurements obtained on Visit 2, Visit 3, and Visit 4, respectively
- EOT = the median of GSP4, GSP5, and GSP6 measurements obtained on Visit 10, Visit 11, and Visit 12, respectively

Note that at each timepoint, GSP will be defined as the sum of both axillae measurements. If 1 axilla value is missing at a timepoint, then the non-missing observed value will be multiplied by 2. The values for baseline or EOT will not be regarded as missing as long as the measurement is available at least for one of the three timepoints.

## 10.2.2 Co-Primary Efficacy Endpoints

The following co-primary efficacy endpoints will be analyzed to assess the efficacy of sofpironium bromide gel, 15%:

- The proportion of subjects achieving at least a 2-point improvement in the HDSM-Ax-7 scale score from baseline to EOT.
- The change in GSP from baseline to EOT.

Note that the assessment of the first co-primary efficacy endpoint will be conducted using 7 of the 11 items on the HDSM-Ax scale. More specifically, the mean of the 2 items in section 1 and the first 5 items in section 2 (7 sub-items in total) will be used. The mean will be derived by taking the sum of 7 item scores and dividing it by 7. For each of the HDSM-Ax sub-items, missing values at EOT will be imputed as described briefly in Section 10.3.1. HDSM-Ax-7 at EOT will be derived from the imputed values. Further details on imputation methods will be provided in the SAP.

#### 10.2.3 Secondary Efficacy Endpoints

The following secondary efficacy endpoints will be analyzed:

- The proportion of subjects achieving at least a 1-point improvement in the HDSM-Ax-7 scale score from baseline to EOT.
- The proportion of subjects achieving at least a 2-point improvement in the HDSM-Ax-7 scale score from baseline to EOT and achieving at least a 70% reduction in GSP from baseline to EOT.

• The proportion of subjects achieving at least a 1-point improvement in the HDSM-Ax-7 scale score from baseline to EOT and achieving at least a 50% reduction in GSP from baseline to EOT.

## 10.2.4 Exploratory Efficacy Endpoints

Exploratory efficacy endpoints to be analyzed include the following:

- The proportion of subjects achieving at least a 1-point improvement in the HDSM-Ax-7 scale score from baseline to Days 8, 15, 22, 29, 36, 41, 42, 43 (EOT), and 57.
- The proportion of subjects achieving at least a 1-point improvement in the HDSM-Ax 11-Item (HDSM-Ax-11) scale score from baseline to Days 8, 15, 22, 29, 36, 41, 42, 43 (EOT), and 57.
- The proportion of subjects achieving at least a 2-point improvement in the HDSM-Ax-7 scale score from baseline to Days 8, 15, 22, 29, 36, 41, 42, 43 (EOT), and 57.
- The proportion of subjects achieving at least a 2-point improvement in the HDSM-Ax-11 scale score from baseline to Days 8, 15, 22, 29, 36, 41, 42, 43 (EOT), and 57.
- The proportion of subjects achieving at least a 1-point improvement in the HDSM-Ax Question 4 score from baseline to Days 8, 15, 22, 29, 36, 41, 42, 43 (EOT), and 57.
- The proportion of subjects achieving at least a 2-point improvement in the HDSM-Ax Question 4 score from baseline to Days 8, 15, 22, 29, 36, 41, 42, 43 (EOT), and 57.
- The proportion of subjects achieving at least a 1-point improvement in the HDSM-Ax Question 5 score from baseline to Days 8, 15, 22, 29, 36, 41, 42, 43 (EOT), and 57.
- The proportion of subjects achieving at least a 2-point improvement in the HDSM-Ax Question 5 score from baseline to Days 8, 15, 22, 29, 36, 41, 42, 43, (EOT), and 57.
- Change in PGI-S from baseline to Days 8, 15, 22, 29, 36, 41, 42, 43 (EOT), and 57.
- PGI-C score on Day 43 (EOT).
- The proportion of subjects achieving at least a 2-point improvement in the HDSM-Ax-11 scale score from baseline to EOT and achieving at least a 70% reduction in GSP from baseline to EOT.
- The proportion of subjects achieving at least a 1-point improvement in the HDSM-Ax-11 scale score from baseline to EOT and achieving at least a 50% reduction in GSP from baseline to EOT.
- The proportion of subjects achieving at least a 2-point improvement in the HDSM-Ax-7 scale score and achieving at least a 70% reduction in GSP from baseline to Days 8, 15, 22, 29, 36, 41, 42, 43, EOT, and Day 57.
- The proportion of subjects achieving at least a 2-point improvement in the HDSM-Ax-11 scale score and achieving at least a 70% reduction in GSP from baseline to Days 8, 15, 22, 29, 36, 41, 42, 43, EOT, and Day 57.
- The proportion of subjects achieving at least a 1-point improvement in the HDSM-Ax-7 scale score and achieving at least a 50% reduction in GSP from baseline to Days 8, 15, 22, 29, 36, 41, 42, 43, EOT, and Day 57.
- The proportion of subjects achieving at least a 1-point improvement in the HDSM-Ax-11 scale score and achieving at least a 50% reduction in GSP from baseline to Days 8, 15, 22, 29, 36, 41, 42, 43, EOT, and Day 57.

- Change in HDSM-Ax-7 scale score from baseline to Days 8, 15, 22, 29, 36, 41, 42, 43 (EOT), and 57 as a continuous measure.
- Change in HDSM-Ax-11 scale score from baseline to Days 8, 15, 22, 29, 36, 41, 42, 43 (EOT), and 57 as a continuous measure.
- The proportion of subjects achieving at least a 70% reduction in GSP from baseline to Days 8, 15, 22, 29, 36, 41, 42, 43, EOT, and Day 57.
- The proportion of subjects achieving at least a 50% reduction in GSP from baseline to Days 8, 15, 22, 29, 36, 41, 42, 43, EOT, and Day 57.
- The rank-based GSP change from baseline to Days 8, 15, 22, 29, 36, 41, 42, 43, EOT, and Day 57.
- The absolute GSP change from baseline to Days 8, 15, 22, 29, 36, 41, 42, 43, EOT, and Day 57.
- The percent change from baseline in GSP from baseline to Days 8, 15, 22, 29, 36, 41, 42, 43, EOT, and Day 57.
- The change in the modified DLQI from baseline to Day 15 and Day 43 (EOT).

